Confounders: pre-defined lists of confounders will be identified for each of the study outcomes. These will be included in separate propensity score logistic equations to minimize confounding by indication. Propensity scores (ps) represent the probability that a patient will receive a specific treatment based on his/her baseline characteristics (5).

Power: according to feasibility counts from CPRD, 4,127 eligible (eGFR<45) bisphosphonate users and 204,528 eligible non-users are available. These numbers provide >90% power to detect as significant a HR of \geq 1.20 for the association between bisphosphonate use and the outcomes in WP1 and WP3, and a HR o \leq 0.85 for the association between bisphosphonate use and fracture risk (WP2). Regarding WP4, the numbers provided by OUHD (>500 bisphosphonate users and >3,000 non-users with eGFR<45 available in the dataset at 31/12/2012) ensure 80% power to detect as significant an expected >25% difference in bone loss between bisphosphonate users and non-users.

Statistical analyses: firstly, logistic equations will be fitted to estimate ps for each of the study outcomes. Secondly, each bisphosphonate user will be ps-matched to 5 non-users using caliper-matching methods. Ps-matching has been shown to be useful to minimize confounding by indication in observational studies involving drugs (i.e.pharmacoepidemiology) (6). Missing confounders will be handle with 10 multiple imputation by chained equations. Finally, time-varying Cox regression models stratified by ps matched sets will be used to study the association between bisphosphonate use and each of the study outcomes in WP1-3; similarly, linear regression modeling will be used to study the relationship between bisphosphonate use and hip bone density change in WP4.

BACKGROUND AND RATIONALE

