The chosen study design is a propensity score-matched retrospective cohort study. This is one of the best pharmaco-epidemiological designs available for the assessment of intended (benefits) and unintended (risks) effects of drugs in observational data. Propensity score-matching will therefore be used to match each eligible bisphosphonate user to 5 non-users, producing matched comparable (in terms of observed baseline characteristics) cohorts.

TARGET POPULATION

The target population of this study will be patients with an eGFR<45 (based on serum creatinine) aged 40 years or older at the age of biochemistry testing.

EXCLUSION CRITERIA

From the population described above, we will exclude those with any of the following exclusion criteria:

- Less than 1 year of follow-up data available within the data source/s.
- CPRD participants with no possible linkage to HES.
- Use of anti-osteoporosis medication/s in the previous year (except calcium and/or vitamin D supplements).
- Use of any (except calcium and/or vitamin D supplements) other anti-osteoporosis medication/s (other than bisphosphonates).

SETTING/CONTEXT

Setting: The proposed study will obtain data from both primary (CPRD) and secondary (HES) care.

Study period: Currently used oral bisphosphonates (alendronate, risedronate and ibandronate) were approved and launched to the market in 1996 onwards. Our study period will therefore cover from 1996 to the latest data extraction for the identified data sources, likely 31/12/2014.

Follow-up: Data from randomized placebo-controlled trials have shown that bisphosphonates are effective to reduce fracture risk only after at least 6 months of continuous use (27). That is not the case though for adverse events, which can be observed immediately after bisphosphonate therapy initiation (14, 17, 28). Therefore, different follow-up windows will be established, as follows:

- Safety outcomes (WP1 and WP3): Patients will be followed from the latest of the following dates
- a) Start of study period
- b) One year of valid data in database
- c) Date of incident prescription of bisphosphonate (after one year of non-use)

until the earliest date of:

- a) The end of enrolment in the database (due to moving out or death)
- b) Date of last data update in the database
- c) Stopping of treatment +30 days (no repeat prescription within 1 month)
- d) Switch of treatment to other (non-bisphosphonate) osteoporosis medication

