- e) Outcome of interest (different date for each study outcome)
- Effectiveness outcomes (WP2 and WP4): Patients will be followed from the latest of the following dates
- a) Start of study period
- b) One year of valid data in database
- c) Date of continued prescriptions of an oral bisphosphonate for 6 months after the date of therapy initiation

until the earliest date of:

- a) The end of enrolment in the database (due to moving out or death)
- b) Date of last data update in the database
- c) Stopping of treatment +180 days (no repeat prescription within 6 months)
- d) Switch of treatment to other osteoporosis medication, with no repeat prescription of oral bisphosphonates within the next 6 months
- e) Incident recorded fracture (WP2) or last BMD measurement available (WP4)

SAMPLING

One of the advantages of routinely collected datasets is that the contained information is readily available, not needing active recruitment. Therefore, all patients eligible (see target population and exclusion criteria above) registered in the chosen data sources will be included.

Sample size/power: According to feasibility counts provided by CPRD, the number of eligible patients (with an eGFR<45 and possible to link to HES) would be of 204,528 subjects, and 34,127 (16.7%) of these received oral bisphosphonate prescriptions. These numbers would provide statistical power to reliably answer each of the study aims, as it can be seen below:

Work-package 1: In a survival analysis (log-rank 2-sided test), accepting 5% type I error and 20% attrition from propensity score matching and loss to follow-up in 2 years, and assuming CKD stage progression rates of 12/100 person-years (29), the available number of participants would provide 90% power to detect an excess risk of CKD progression of 10% or more (HR \geq 1.10) associated with oral bisphosphonate use.

Work-package 2: In a log-rank (2-sided) test, and accepting 5% type I error and 20% drop-out, with 2 years of follow-up and an expected fracture rate of 103/10,000 person-years in CPRD data (30), the available sample size would provide 90% power to detect a fracture reduction of at least 15% (HR≤0.85) amongst oral bisphosphonate users (compared to non-users).

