Propensity Score matching: Propensity scores represent the probability that a patient will receive the drug of interest (i.e. oral bisphosphonates) according to their baseline sociodemographics and clinical characteristics. Multivariable logistic regression equations will be used to calculate one propensity score for each of the study outcomes of interest (36). Prespecified predictors of each of these outcomes will be included in each of these equations (37). Finally, the created propensity scores will be used to match bisphosphonate users to comparable non-users with a caliper matching technique with a maximum caliper width of 0.02 standard deviations (SDs). In short, this means that bisphosphonate non-users will only eligible to be matched if their propensity score falls within a bandwidth of 0.02 SDs of the bisphosphonate user subject's propensity score. This method has been shown to be the most efficient to minimize confounding by indication in pharmacoepidemiological studies (6) and typically excludes the small proportion of patients with extremely high or extremely low risk

for the outcome that are not present in both intervention and comparator patient samples. Covariate balance achieved through PS matching will be assessed using absolute standardized difference in means or proportions.

Some confounders, such as smoking, alcohol drinking, body mass index might not be completed. We will impute them for the propensity score (logistic) models using multiple imputation by chained equations (MICE) methods. 10 imputed datasets will be used. For each imputed dataset, a ps matched dataset will be identified and analysed as per study outcome separately. Outcome estimates of 10 ps imputed datasets will be then combined using Rubin's rules to obtain an overall outcome estimate (46).

Absolute rates of study outcomes: The crude and age and sex specific incidence rates (and 95% confidence intervals) of each of the events will be estimated separately in the cohort of oral bisphosphonate users and amongst propensity score-matched non-users assuming a Poisson distribution. Kaplan-Meier plots will be created to show the predicted cumulative probability of each of the study endpoints according to bisphosphonate use.

In addition, annualized eGFR (secondary outcome in WP1) and BMD (WP4) changes and 95% confidence intervals will be reported.

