Immortal time bias and time-varying exposure: Immortal time bias (ITB) is a common issue in pharmaco-epidemiology. In brief, ITB appears when in a study the event of interest cannot occur for a certain time span due to study design and/or data analysis methods used (26). In cohort studies, immortal time typically arises when the definition of drug use involves a delay or wait period during which follow-up time is accrued—for example, waiting for a prescription or drug dispensation after discharge from hospital when the discharge date represents the start of follow-up (38).

A number of methods are available to avoid ITB. We will, in our study, use time-varying exposures, where in a survival analysis the time previous to index date for drug users (i.e. the time before first prescription of oral bisphosphonates) is reclassified as drug non-user personyears. We have extensive expertise using this method (39-41), which has been shown to be the most efficient to avoid ITB in pharmaco-epidemiological studies (42).

Hazard ratios: We will use proportional hazards Cox regression modelling to estimate the Hazard Ratio (HR) and 95% Confidence Intervals for each of the outcomes of interest according to bisphosphonate use. To account for the matched cohort approach proposed, we will use Cox regression stratified by matched sets.

The proportional hazards assumption will be checked using clog log plots. Alternative models, e.g. parametric survival models and weighted Cox regression(43) will be considered. The final decision of the alternative modelling techniques will depend on the availability of a suitable function to describe the hazards distribution.

If mortality rates are different amongst bisphosphonate users and matched non-users, Fine and Gray survival analyses (44) will be used instead, to account for a competing risk with death.

Failing to do so would results in a biased estimation of the excess/reduced risk of the events of interest amongst bisphosphonate users (45).

Beta coefficients: Longitudinal analysis will be used to study the association between bisphosphonate use and annualized changes of both eGFR (secondary outcome in WP1) while linear regression modelling will be used to study the association between bisphosphonate use and changes of BMD between two observed time points (WP4). Beta coefficient and 95% confidence intervals will be reported for the effect of bisphosphonate use on both outcomes.

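### The protocol's own counts do not allow complete 1:5 matching without replacement, and if smaller sets are kept the pooled rates, Kaplan-Meier plots and balance checks need set weights

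*Protocol*

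**What the plan says.** **Ratio.** The matching ratio is fixed throughout. In the Summary of Research (Statistical analyses), "each bisphosphonate user will be ps-matched to 5 non-users using caliper-matching methods". Under Study Design, propensity score matching is used to "match each eligible bisphosphonate user to 5 non-users, producing matched comparable (in terms of observed baseline characteristics) cohorts". Table 1 and the WP4 sample size also assume five non-users per user.

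**Counts.** Sampling (Sample size/power) gives "204,528 subjects, and 34,127 (16.7%) of these received oral bisphosphonate prescriptions". The Summary (Power) instead gives "4,127 eligible (eGFR<45) bisphosphonate users and 204,528 eligible non-users are available". Data Collection repeats a figure above 34,000 users.

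**Matching.** Data Analysis (Propensity Score matching) sets a maximum caliper of 0.02 SD and expects matching to exclude only a small proportion of patients at the extremes. It does not state whether matching is with replacement, or what happens to a user with fewer than five matches.

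**Outputs by group.** Data Analysis (Absolute rates of study outcomes) plans crude and age- and sex-specific rates "estimated separately in the cohort of oral bisphosphonate users and amongst propensity score-matched non-users assuming a Poisson distribution", and Kaplan-Meier plots by bisphosphonate use. For balance: "Covariate balance achieved through PS matching will be assessed using absolute standardized difference in means or proportions". No set weights are mentioned and none are excluded.

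**Model.** Data Analysis (Hazard ratios) accounts for the matching by stratifying the Cox regression by matched set. If mortality differs between groups, Fine and Gray analyses replace it, with no stratification by set stated for them.

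**The concern.** Two pooled matched groups are comparable without weights only if every user brings the same number of non-users. Non-users are scarcest where the propensity score is high, that is, among patients with the strongest indication for treatment. If those users bring one or two non-users and low-score users bring five, the pooled non-users lean towards low scores. Where the score predicts fracture, crude rates and Kaplan-Meier curves would then show more fractures in users even if the drug did nothing.

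These rates and curves are the absolute benefit and harm figures that NICE and the MHRA would read, and they could disagree with the hazard ratio stratified by set. The balance table would report imbalance that does not exist within sets and might prompt a needless change to the propensity model. The alternative, keeping only complete sets of five, removes this problem but loses users and power, and the loss falls mainly on high-propensity patients.

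**Working it through.** **1. The plan's own figures, which rest on full 1:5 sets.**

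Table 1 follows from d = (1.960 + 1.282)² / [(1/6)(5/6)(ln HR)²] and users = d / p̄ / 6 / 0.8. Here p̄ is the mean of the 2-year incidence ci and 1 − (1 − ci)^HR. For 2% and HR 1.2, d = 2,276 and p̄ = 0.02198, giving 21,577 users against 21,578 stated. All 25 cells reproduce closely.

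For WP2 (103 per 10,000 person-years, 2 years, HR 0.85, 20% drop-out) the same method needs 2,865 events, or about 30,000-31,600 users depending on how the two incidences are averaged. With 34,127 users the power is 92.0-93.3%, so the stated 90% holds if every set is complete.

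**2. Can every set be complete?**

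- Non-users available: 204,528 − 34,127 = 170,401, and 170,401 / 34,127 = 4.99 per user.
- Non-users needed: 5 × 34,127 = 170,635.
- Shortfall: 234 (0.14%) before the caliper removes anyone.

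The overall shortfall is tiny. What matters is where non-users are scarce. With the Summary's counts, 204,528 / 4,127 gives about 50 per user and the scarcity nearly disappears. The internal evidence favours the larger user count: 34,127 / 204,528 = 16.7%, the percentage printed beside it, and Data Collection agrees.

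**3. The mechanism by hand (illustrative inputs).**

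Suppose 30% of users are in a stratum with twice the risk and get one non-user each, while the rest get five. Relative to the low-risk stratum:

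- users: 0.7 + 0.3 × 2 = 1.30
- non-users, unweighted: (0.7 × 5 + 0.3 × 1 × 2) / (0.7 × 5 + 0.3 × 1) = 4.1 / 3.8 = 1.079
- null ratio: 1.30 / 1.079 = 1.205
- non-users weighted by 1/k, where k is the number of non-users in the set: 0.7 + 0.3 × 2 = 1.30, so the ratio is 1.00

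Other choices of these three inputs gave 1.05-1.25.

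**4. Size under a range of assumptions.**

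The protocol gives neither the strength of the propensity model nor its link to fracture risk, so both were varied. Matching was simulated without replacement, up to five non-users within 0.02 SD, with no drug effect, the sample-size section's counts and c-statistics of 0.60-0.85. Scarce non-users were shared across sets, giving a mean set size of 2.9-4.3.

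| Assumed rate ratio per SD of the propensity linear predictor | Null rate ratio, unweighted | Weighted 1/k |
|---|---|---|
| 1.1 | 1.02-1.04 | 1.00 |
| 1.25 | 1.04-1.09 | 1.00 |
| 1.5 | 1.09-1.17 | 1.00 |
| 2.0 | 1.16-1.33 | 1.00 |

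The unweighted standardized difference of the linear predictor was about 0.18-0.52, and 0.00 with weights.

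Other counts and algorithms, at 1.5 per SD where a rate ratio applies:

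- Summary counts (4,127 users): 1.005-1.054.
- 34,127 users with 204,528 non-users (5.99 per user): 1.135 and 1.166 at c-statistics of 0.70 and 0.80. A modest overall surplus therefore does not cure scarcity at high scores.
- Sets filled to five one at a time: nearly every user has five or none, and the ratio stays near 1.00.

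**5. If only complete sets of five are kept.**

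The null ratio is 1.00. Users retained are about 51-85% if sets are filled one at a time (c-statistics 0.60-0.85) and about 27-44% if non-users are spread evenly (c-statistics 0.61-0.78), so roughly 30-85% overall.

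WP2 power is Φ(0.1625 × √(d × 5/36) − 1.96), with set loss applied on top of the 20% drop-out. At 85% retained, d = 2,769 and power is 89%. At 52%, d = 1,694 and power is 70%. It is lower still if fewer users remain.

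**The case against.** The strongest reply is that the protocol writes 1:5 and nothing else. It never says that smaller sets are kept or that weights are omitted. Complete sets need no weights, and the weighting of descriptive output is commonly left to a statistical analysis plan, which is not shown. The 20% attrition for matching and loss to follow-up in WP1 could absorb users who cannot be fully matched: after it, only 0.8 × 34,127 × 5 = 136,508 non-users are needed.

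Much of this stands. Silence on weights alone would not be a finding. What remains is that the fixed ratio cannot be met for all users from the protocol's main counts without replacement, and that no rule covers the shortfall. Dropping incomplete sets loses 15-49% of users even under the more favourable algorithm. That is hard to square with the small exclusion the protocol expects, or, at most c-statistics, with 20% attrition that must also cover loss to follow-up.

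A reader might infer more than the documents support:

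- **That fracture rates will be about 20% too high in users.** Values near 1.20 arise only with particular assumed inputs. The range runs from about 1.00 to 1.33 across algorithms, gradients and counts.
- **That the main result is confounded.** The Cox hazard ratio is stratified by set and tolerates unequal sets. Setting a crude ratio against the 15% reduction for WP2 compares a descriptive figure with a power target for a different analysis.
- **That the eGFR model pools the groups.** The text says only "Longitudinal analysis will be used to study the association between bisphosphonate use and annualized changes" and does not mention pooling, set terms or weights.
- **That imbalance would be hidden.** An unweighted standardized difference would flag it. Age- and sex-specific rates also remove part of it, though not the part due to prior fracture or steroid use.

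Matching with replacement would change the feasibility arithmetic, but it is not stated.

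**Conclusion.** The point holds conditionally. With 34,127 users among 204,528 eligible patients, complete 1:5 caliper matching without replacement is not attainable for all users. The plan then leads to one of two results:

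- smaller sets are kept, and unweighted pooled rates, curves and standardized differences are biased, with a null rate ratio of about 1.02-1.33 when non-users are shared across sets and near 1.00 when sets are filled one at a time; or
- only complete sets are kept, with no such bias but roughly 30-85% of users remaining and losses concentrated at high propensity scores.

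These sizes rest on assumed c-statistics of 0.60-0.85, assumed rate ratios of 1.1-2.0 per SD, matching without replacement and the larger user count. With the Summary's counts, at 1.5 per SD, the bias is about 1.01-1.05. The hazard ratio from the set-stratified Cox model is not affected. The exposed results are the absolute figures, the balance check and any comparative model not stratified by set.

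**What to change.** In Data Analysis (Propensity Score matching and Absolute rates of study outcomes):

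- State that each user is matched to one to five non-users, and whether matching is with replacement.
- Weight each matched non-user by 1/(number of non-users in the set), with robust standard errors, in the incidence rates, Kaplan-Meier plots, standardized differences and any comparative model not stratified by set, for example Fine and Gray if it is used.
- Report the distribution of set sizes.
- Reconcile 4,127 users in the Summary with 34,127 in Sampling and above 34,000 in Data Collection, and say whether 204,528 counts all eligible patients or non-users only.

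The cost is one weight variable, a few sentences and slightly wider intervals for the weighted non-user rates. The set-stratified Cox model needs no change.

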DISSEMINATION AND PROJECTED OUTPUTS
OUTPUTS
DISSEMINATION
MANAGEMENT PLAN
REGULAR COMMUNICATION
APPROVAL BY ETHICS COMMITTEES
PATIENT AND PUBLIC INVOLVEMENT26
REFERENCES
APPENDIX 1

SUMMARY OF RESEARCH

AIM/S

Although osteoporosis and fragility fractures are common amongst CKD patients, the effectiveness and safety of first-line anti-fracture therapies (bisphosphonates) for this population are still unclear. We therefore aim to study the association between oral bisphosphonate (OB) use in stage ≥3B CKD patients and the following outcomes: CKD progression (stage worsening or entering renal replacement therapy or transplant) (WP1), clinical fracture/s (WP2), adverse events (hypocalcaemia or hypophosphatemia, upper gastro-intestinal events, and acute kidney injury) (WP3), and axial bone mineral density (WP4).

METHODS

Data sources: the primary data source for WP1-3 of our study will be the Clinical Practice Research Datalink (CPRD), linked to the Hospital Episodes Statistics (HES). Data from the Danish Odense University Hospital Database (OUHD) will be used for WP4.

Study participants: all patients registered in CPRD or in OUHD, aged \geq 40 years, with an eGFR<45, and with \geq 1 years of follow-up data available will be included. Users of bisphosphonates in the year before eGFR testing, as well as CPRD participants with no possible linkage to HES data will be excluded.

Exposure: Users of oral bisphosphonates will be identified from primary care prescriptions (CPRD) or pharmacy dispensations (OUHD).

Outcomes: WP1: CKD progression will be defined as stage worsening (according to eGFR as recorded in CPRD) or initiation of renal replacement therapy/transplant (HES).

Study outcomes for WP2-3 will be ascertained using previously validated lists of READ/OXMIS (CPRD) (1-3) or ICD-10/OPCS (HES) (4) codes. The main study outcomes will be: all clinical fractures excluding the skull/face and digits, which are not considered to be osteoporotic (WP2), and adverse events (hypocalcaemia/hypophosphatemia requiring hospital admission, upper gastro-intestinal events, and hospitalization for acute kidney injury) for WP3. WP4: annualized hip bone mineral density percentage change, as measured using DXA scan, will be measured.

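### WP1 counts crossings of an eGFR stage boundary, but the stated Cox model has no baseline eGFR or stage, and matching as described does not secure balance in distance to that boundary

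*Protocol*

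**What the plan says.** - **Outcome** (Summary of Research, Outcomes): "CKD progression will be defined as stage worsening (according to eGFR as recorded in CPRD", or as initiation of renal replacement therapy or transplant.
- **Model** (Data Analysis, Hazard ratios): a Cox model for each outcome according to bisphosphonate use. "To account for the matched cohort approach proposed, we will use Cox regression stratified by matched sets". No other covariate is named.
- **Matching** (Data Analysis, Propensity Score matching): one score per outcome, built from prespecified predictors of that outcome, with 1:5 caliper matching on that single score. The predictors are not listed. "Covariate balance achieved through PS matching will be assessed using absolute standardized difference in means or proportions". No limit is given.
- **CKD stage** (Sensitivity analyses): appears only as an interaction, with stratified results if it is significant.
- **Size** (Sampling, Work-package 1): "90% power to detect an excess risk of CKD progression of 10% or more", "accepting 5% type I error and 20% attrition from propensity score matching and loss to follow-up in 2 years", with 12 events per 100 person-years. The Summary gives HR 1.20 for WP1, not 1.10.
- **Prescribing** (Background and Rationale): alendronate is not recommended below eGFR 35, nor ibandronate and risedronate below 30.

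**The concern.** When the event is defined by a fixed threshold, a patient just above it and a patient at the top of the stage have very different risks whatever the drug does. Two matched groups can have nearly the same mean eGFR, yet one can sit slightly nearer its next boundary. The WP1 hazard ratio would then reflect starting position as well as bisphosphonate use. WP1 is a safety question whose results are to go to MHRA and NICE, so a false excess and a hidden excess both matter.

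Matching on one scalar score allows eGFR, and even stage, to differ within a set. That is no bias in itself if the differences average out. They average out only as well as the score captures how prescribing depends on eGFR.

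**Working it through.** **1. The protocol's own power figure.** Inputs: 34,127 users, 1:5 matching, 20% attrition, rate 0.12 per person-year, 2 years, HR 1.10, two-sided 5%.

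- Users: 34,127 × 0.8 = 27,302. Non-users: 5 × as many, about 136,508.
- Events: 27,302 × (1 − exp(−0.264)) + 136,508 × (1 − exp(−0.24)) = 6,335 + 29,127, about 35,460.
- √(events × 1/6 × 5/6) = 70.2. Then ln(1.10) × 70.2 − 1.96 = 4.73, so power is above 99.9%, not 90%.
- HR detectable at 90% power: exp(3.24/70.2) = 1.047.

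The Summary's 4,127 users give about 4,290 events and 64% power for HR 1.10. On the Sampling section's counts, a bias of even 5% would tend to appear statistically significant.

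**2. Closed form for the gap.** Assume stages of width W = 15, distances spread evenly within stage, and linear decline r.

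- Rate = r/W, so r = 0.12 × 15 = 1.8 ml/min/year.
- Two-year crossings = 3.6/15 = 24%.
- A 10% rise in crossings needs users to start 0.1 × 3.6 = 0.36 ml/min nearer the boundary.
- At an assumed eGFR SD of 5 to 10, that is a standardized difference of 0.04 to 0.07.

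**3. Simulation of a given gap.** True HR 1, six-monthly readings for 2 years, decline calibrated to 12/100 person-years, four baseline distributions, slope SD 0 or 3, reading noise SD 0, 2 or 4. The HR is a visit-stratified Mantel-Haenszel estimate, without and with baseline eGFR in 0.5-unit strata. One distribution (45 minus an exponential with mean 6), users shifted by 0.4 ml/min:

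| Noise SD | Slope SD | Within-stage shift: HR | Same, eGFR conditioned on | Whole-distribution shift: HR |
|---|---|---|---|---|
| 0 | 0 | 1.109 | 1.000 | 1.073 |
| 0 | 3 | 1.087 | 1.003 | 1.058 |
| 2 | 3 | 1.094 | 1.012 | 1.036 |
| 4 | 3 | 1.093 | 1.026 | 1.042 |

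Over all scenarios:

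- A within-stage gap of 0.4 gives HR 1.08 to 1.15, and HR 1.10 is reached at about 0.27 to 0.5 ml/min.
- A 0.4 shift of the whole distribution gives about 1.00 to 1.08. Some users then fall into the next stage and start far from its boundary.
- After conditioning on stage and baseline eGFR, the within-stage case gives 1.00 without noise, 1.01 to 1.02 at noise SD 2, and 1.02 to 1.04 at noise SD 4.

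**4. Can such a gap arise with eGFR in the score?** Assume no drug effect, prescribing odds multiplied by 0.5 to 1.0 below 35 and by a further 0.5 to 0.8 below 30, two eGFR distributions over 15 to 45, score weighting in place of matching, and 2-year incidence of 12 to 22% (the protocol's rate implies 1 − exp(−0.24) = 21%).

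- eGFR as a linear term: overall standardized difference at most 0.01, yet users were 0.1 to 0.6 ml/min nearer their boundary; HR 0.98 to 1.20. A straight line through a step leaves users over-represented just above 30 and under-represented just below it, and both put them nearer a boundary.
- eGFR as stage only: standardized difference at most 0.11; HR 0.72 to 1.01. The step at 35 leaves users over-represented in the upper part of stage 3B, farther from the boundary.

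A second run, also stepped at 35 and 30, gave 0.99 to 1.15 (linear) and 0.71 to 0.99 (stage only). Conditioning on baseline eGFR brought the HR to 0.98 to 1.02.

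**The case against.** The strongest reply is that the protocol already covers this. Each score is to hold predictors of its own outcome, so baseline eGFR belongs in the WP1 score, and the covariate list may sit in an analysis plan that is not shown. If eGFR is modelled well, chance imbalance is small: SD × √(1/27,302 + 1/136,508) = 0.03 to 0.07 ml/min at an SD of 5 to 10. Annualized eGFR change is a secondary outcome that does not depend on boundaries, and a CKD-stage interaction is planned.

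Much of this stands. A reader might infer that the plan ignores baseline eGFR; the documents do not support that. A reader might also infer that any difference of a few tenths in mean eGFR imitates the 10% excess; that holds only for distance within stage. Nor do the documents show that the error would exaggerate harm. The contraindications could equally put users farther from the boundary and hide an excess.

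What the reply does not answer is step 4: eGFR can be in the score, and the overall balance check can look excellent, while the HR is off by 10% or more. The Rosenbaum analysis is planned for unobserved confounders, and eGFR is observed. The Hazard ratios text is a stated model, so this point improves what is written and does not ask for missing detail.

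**Conclusion.** The point holds as an inexpensive strengthening of the WP1 analysis. The protocol defines an event driven by distance to a boundary and states a model without that distance. Its matching and balance check do not secure comparability on it. A within-stage gap of about 0.3 to 0.5 ml/min moves a null HR by about 10% in either direction.

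Stage width, eGFR distribution, rate of decline, reading noise and the size of the prescribing steps are assumptions, not figures from the protocol. Whether a gap of this size will occur is not known. The benchmark of 10% is the Work-package 1 figure; the Summary's HR 1.20 conflicts with it, and only the more extreme assumptions reach 20% or more. It would also go too far to expect adjustment to remove the bias entirely: a noisy single baseline reading leaves up to about 4%. Loss of power is not the argument, because on the Sampling section's counts power is already ample.

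**What to change.** - In Data Analysis, Hazard ratios, for WP1: add baseline CKD stage and continuous baseline eGFR, flexible within stage, to the set-stratified Cox model. Use the last value on or before the index date, or the matched index date for non-users. Carry the same terms into any Fine and Gray model used instead.
- In Data Analysis, Propensity Score matching: report eGFR balance within each stage, in ml/min, as well as the overall standardized difference.

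Cost: one or two model terms, using a measurement already required for entry. The one real piece of work is assigning an index date to matched non-users, because the Follow-up section gives only users a treatment-based start.
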